#### **5.2 SUBJECT EXCLUSION CRITERIA**

A subject will be excluded from participating in the study for any of the following reasons:

- E.1 Subjects who are currently breastfeeding or have discontinued breastfeeding fewer than 6 months prior to screening.
- E.2 Subjects who are pregnant or plan to become pregnant during the course of the study.
- E.3 Subjects who have undergone other stress urinary incontinence treatments, excluding behavioral modifications (e.g., Kegel exercises).
- E.4 Urinary Tract Infection (UTI) at the Screening or Randomization Visit based on the results of a urine dipstick. If the subject has a UTI at the Screening or Randomization Visit they may be treated with antibiotics, at the Investigator's discretion, and return within 7 days after UTI treatment completion. Subjects may return once, within 7 days after completion of UTI treatment.
- E.5 Abnormal, clinically significant laboratory results at the Screening Visit (as determined by the Investigator).
- E.6 History of any condition, illness, or surgery that might confound the results of urinary incontinence assessment, including, but not limited to:

- a. Prominent (i.e. greater than Stage II as defined by the International Continence Society) pelvic organ prolapse (e.g., cystocele, rectocele) as determined by investigator.
- b. Neurological disorders (e.g., multiple sclerosis, Parkinson's disease)
- c. History of recurrent Urinary Tract Infections (UTI)
- d. Vesicoureteral reflux
- e. Bladder stones at time of enrollment or history of recurrent bladder stones
- f. History of or current diagnosis of bladder tumors
- g. Interstitial cystitis

E.7 Has any implantable electrical device [e.g., implantable pacemaker, automatic implantable cardioverter-defibrillator (AICD)].

E.8 Subjects with conditions that may pose unreasonable risks, including but not limited to:

- a. Concurrent infection (e.g., active UTI, cystitis, urethritis)
- b. Coagulation abnormalities
- c. Abnormal kidney function
- a. Uncontrolled diabetes

E.9 Medical or immunological condition, including, but not limited to:

- a. Uncontrolled cardiovascular, respiratory, neoplastic, infectious, and/or endocrinological condition that could impact the subject's ability to complete the trial.
- b. Untreated chronic abdominal/pelvic pain disorder [including, but not limited to, dyspareunia, vaginismus, endometriosis, vulvovaginal atrophy (VVA), genitourinary syndrome of menopause (GSM), irritable bowel syndrome, or Crohn's disease].
- c. Untreated medical condition or medication that, in investigator's opinion, may interfere with adequate wound healing response (e.g., congenital connective tissue disease) or the subject's ability to complete the clinical trial requirements.
- d. Untreated active malignancy or undergoing treatment (using chemotherapeutic agents, radiation therapy, and/or cytostatic medications) that may interfere with adequate wound healing response or the subject's ability to complete the trial.
- e. Untreated acute or chronic vaginal or vulvar disorder including, but not limited to, vulvovaginal atrophy/GSM; pain, including provoked/generalized vulvodynia, vulvar vestibulitis, dysesthetic vulvodynia, or vulvar dystrophy; current/chronic papulosquamous vulvar dermatoses (e.g., psoriasis, lichen planus, tinea cruris, lichen sclerosis, seborrheic dermatitis, contact/irritant dermatitis, lichen simplex, eczema); bullous dermatoses; systemic diseases with potential involvement of vulva; genital warts; past/current vaginal or vulvar radiotherapy or brachytherapy.
- f. Active genital herpes.
- g. Active genital/pelvic infection (e.g., gonorrhea, chlamydia).
- h. Active yeast infection. If the subject has an active yeast infection at the Screening or Randomization Visit they may be treated with an antifungal, at the Investigator's discretion, and return within 7 days after yeast infection treatment completion. Subjects may return once, within 7 days after completion of yeast infection treatment.

E.10 Chronic use of anti-inflammatory drugs, including ibuprofen, aspirin, and steroids (excluding aspirin that is taken for cardiovascular prophylaxis).

E.11 Taking any new medication, including herbal supplements and those taken in teas (< 1 month) that affects urination, or change in the dosage of any medication that affects urination within 1 month of Screening. Dosage should not change for the remainder of the study unless medically necessary.

E.12 Subjects who have started or changed dose of local vaginal hormones <6 weeks before Screening.

E.13 Subjects who have started pelvic floor physical therapy within the last 3 months.

E.14 Undergone previous elective surgical or non-invasive procedure(s) in the vaginal canal (including the Viveve Treatment or any other genital radiofrequency treatment; injectable bulking agent, cosmetic, laser, surgical, and/or genital enhancement procedure). Including previous dilation and cuterage within 12 months of the subject's Pre-Screening Visit.

E.15 Not sterilized (or partner not sterilized/infertile), or not willing to use an acceptable method of birth control started at least 3 months prior to screening and to be continued throughout the duration of the study [e.g., barrier method, intrauterine device, hormonal therapy (subcutaneous, injectable, or

oral contraceptive)]. Rhythm and withdrawal are not considered acceptable forms of contraception.

- E.16 Participated in another clinical study (drug or device) within 30 days of screening, or is not willing to abstain from participating in other clinical studies for duration of trial. If participation was in an investigational drug study (i.e., receiving or has received investigational product), subject must wait 30 days, or 5 times the investigational drug half-life, whichever is longer, prior to Screening.
- E.17 Subject is employed by Viveve or participating investigative sites.

### **5.3 SUBJECT WITHDRAWAL CRITERIA**

A subject may be withdrawn if any of the following occur during the study:

- W.1 Subject requests withdrawal from the study
- W.2 Subject refuses to comply with required study procedures
- W.3 Use of any additional experimental drug or device, or participation in another clinical trial
- W.4 The study sponsor terminates the study site or the study

Subject participation in this trial is voluntary. If a subject decides to participate, she is free to withdraw her consent and to discontinue participation in the trial at any time and for any reason without prejudice to her or effect on her medical care by the physician or the institution. Subjects who withdraw consent after enrolling will be followed until time of withdrawal. In all cases of withdrawal, the reasons for withdrawal must be recorded. If more than one reason is cited for termination, study personnel should identify the most significant reason. Subjects who are withdrawn from the study will not be replaced.

At the discretion of the Principal Investigator or trial Sponsor, Subjects may be removed from this trial due to unanticipated circumstances. A Study Exit Form will be completed for all subjects screened, randomized and treated in the study to document the final disposition of the subjects regardless of whether the subject screen-failed and/or withdrew early or not, as well as the reason(s) the subject was excluded or withdrew from the study, if available.

If a subject does not return for a scheduled visit, every effort should be made to contact the subject and document subject outcome. Subjects will only be considered lost to follow-up if study personnel are unable to communicate with the subject by three separate attempts; attempts may be made via email, phone/text, and/or certified letter. A subject who fails to keep appointments or who refuses to provide any end-of-study information will be documented as lost to follow-up. Subjects who withdraw from the study prior to being randomized will be replaced. Any subject who withdraws from the study after randomization will not be replaced.

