### 9.3 PREGNANCY REPORTING (WHEN APPLICABLE)

During the course of the study, subjects will be instructed to contact the study site immediately if they suspect they might be pregnant. The Investigator should notify Viveve of any pregnancy within 72 hours, and include the following information in the notification:

- Initial pregnancy notification
- Ultrasound (preferably transvaginal) between 6-12 weeks gestation when possible
- Quantitative  $\beta$ HCG
- Follow-up pregnancy notification as new information becomes available
- Other appropriate follow-up procedures should be considered if indicated

Protocol-required procedures for study discontinuation should be performed unless contraindicated by pregnancy. The Pregnancy Reporting CRF should be completed for any subject who becomes pregnant during her participation in the study. Additionally, the study site will make every reasonable effort to follow, until delivery or termination of the pregnancy, subjects who become pregnant during the course of the study. In the case of induced or spontaneous abortion, the aborted fetus can be assessed by gross visual inspection unless there are pre-abortion laboratory findings suggestive of a congenital anomaly.

Pregnant subjects will be followed until pregnancy resolution (delivery or otherwise). Adverse events will be collected throughout the subject's participation in the trial.

Pregnancies will NOT be routinely reported as an AE or SAE. However, any pregnancy-related events that meet the definition for an AE or SAE should be reported accordingly. Pregnancy outcomes that are classified as SAEs are:

- Spontaneous abortion, including miscarriage and missed abortion
- Congenital anomaly/birth defect
- All neonatal deaths that occur within 1 month of birth should be reported, without regard to causality, as SAEs
- Any infant death after 1 month that the Investigator, or qualified designee, assesses as possibly related to the *in utero* exposure to the investigational device

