#### **11.6 STUDY CLOSURE/TERMINATION**

The study may be stopped, if in the opinion of Viveve, there is sufficient reasonable cause. Written notification documenting the reason for study termination will be provided to the Principal Investigator by Viveve. When terminating the study, Viveve and the Principal Investigator will ensure that adequate consideration is given to the protection of the study subjects' interests. Examples of sufficient reasonable cause include:

- Failure to screen subjects,
- Protocol violations,
- Inaccurate or incomplete data collection or recording,
- Unsafe or unethical practices, and
- Any subject safety considerations.

The Principal Investigator is then required to notify the Institutional Review Board/Ethics Committee of the trial termination and to submit to Sponsor in a timely manner all requested Subject and trial data.

Study closure visits will be conducted at all clinical sites in order to review record retention requirements, device disposition requirements, etc., with site personnel. A trial monitor will ensure that all trial files have been appropriately completed and all data have been entered into the EDC system and all queries are resolved. The trial files will then be inventoried and placed in an archiving box for their conservation. Return of investigational devices and related equipment to the Sponsor will be arranged and disposal of any other study supply will be performed. Appropriate inventories will be completed and closed.

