##### 5.1.1.1 Full Analysis Set

The Full Analysis Set (FAS) includes all randomized subjects and is also known as the intention-to-treat (ITT) population. The FAS will be used for all efficacy analyses.

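### Section 5.3 permits withdrawal from follow-up after a one-time treatment and plans no Month 6 pad test afterwards, although the primary analysis needs one from every randomized woman

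*Protocol*

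**What the plan says.** **Grounds for withdrawal.** Protocol 5.3 opens with "A subject may be withdrawn if any of the following occur during the study". The grounds beyond the woman's own request are "W.2 Subject refuses to comply with required study procedures", "W.3 Use of any additional experimental drug or device, or participation in another clinical trial" and "W.4 The study sponsor terminates the study site or the study". A separate sentence adds: "At the discretion of the Principal Investigator or trial Sponsor, Subjects may be removed from this trial due to unanticipated circumstances". Those circumstances are not defined.

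**What follows withdrawal.** Section 5.3 says that a woman who withdraws consent is followed up to that point. It plans no later assessment for the other grounds. It asks for a Study Exit Form, and it does not replace anyone who leaves after randomization.

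**What other sections say.** Protocol 4.2.9 gives withdrawal of consent as the only reason to exit before the 6-month visit. Protocol 8.5.3 keeps a woman whose procedure was cut short in follow-up for the full 6 months. Protocol 4.2.8.2 records other therapies and interventions during participation. Protocol 9.3 states: "Protocol-required procedures for study discontinuation should be performed unless contraindicated by pregnancy". Table 1 and sections 4.2.7, 4.2.9 and 5.3 define no such procedures.

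**What the analysis needs.** SAP 5.1.1.1: "The Full Analysis Set (FAS) includes all randomized subjects and is also known as the intention-to-treat (ITT) population". SAP 5.2 analyses the Month 6 change in 1-hr pad weight in this set, with about 100 imputations under missing at random. The variable list in the SAP code holds only treatment, site, baseline pad weight and the change itself. Both confirmatory analyses use observed cases.

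**The concern.** In a trial of continuing treatment, a withdrawal rule can serve to stop exposure. Here all exposure takes place on Day 1 (Protocol 4.2.4), so a withdrawal under W.2, W.3 or the discretionary sentence can only end data collection. An analysis of all randomized women still needs the Month 6 value from the woman concerned.

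Two things are at stake. The first is precision: the planned power is quoted on all 99 randomized women, with no allowance for loss. The second is bias. A woman who enters another trial, tries another product or tires of study procedures may do so because she has not improved. The imputation model cannot see this, because it contains nothing measured after treatment, not even the Month 3 pad weight. No analysis under a missing-not-at-random assumption is planned that would show how much it matters.

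**Working it through.** **1. Rules side by side.**

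| Event after Day 1 | Protocol 5.3 | Protocol 4.2.9 | Month 6 pad test planned afterwards? |
|---|---|---|---|
| Withdraws consent | leaves | leaves | no, and none can be required |
| Refuses a procedure (W.2) | may be withdrawn | not a stated reason | no |
| Other product or trial (W.3) | may be withdrawn | not a stated reason | no |
| Discretionary removal | may be removed | not a stated reason | no |
| Site or study terminated (W.4) | may be withdrawn | not a stated reason | no |

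The loss is avoidable for W.3, for discretionary removal, and for W.2 when the refused procedure is something other than the pad test. Under W.4 it is avoidable only if a single site closes and Visit 5 can be arranged elsewhere.

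**2. What imputation can recover.** The imputation uses treatment, site and baseline, which are also the terms of the ANCOVA. With no further variable to predict a missing Month 6 value, it returns essentially the observed-case information. Power after loss is therefore well approximated by power on the women observed.

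**3. The plan's own power.** Inputs from Protocol 10.1: two-sided 5% t-test, 50% against 30% reduction (difference 20), SD 28 or 33, 66 active and 33 sham. The noncentrality is difference / (SD × √(1/n₁ + 1/n₂)), and √(1/66 + 1/33) = 0.2132.

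- SD 28: 20 / (28 × 0.2132) = 3.350. With 97 df and critical value 1.985, power is 91.3% (plan: about 90%).
- SD 33: 20 / (33 × 0.2132) = 2.843. Power is 80.4% (plan: about 80%).

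The plan's figures reproduce, with every randomized woman evaluable.

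**4. Power after loss.** The documents give no withdrawal rate. The shares below are assumptions, applied equally to both arms.

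| Share lost | Active : sham observed | Power, SD 28 | Power, SD 33 |
|---|---|---|---|
| 0% | 66 : 33 | 91.3% | 80.4% |
| 5% | 62.7 : 31.35 | 89.8% | 78.3% |
| 10% | 59.4 : 29.7 | 88.2% | 76.0% |

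Keeping 99 evaluable by recruitment instead would need 99 / 0.95 = 104.2, so 105 women, or 99 / 0.90 = 110.

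**5. Extreme case.** Suppose one site filled to its cap supplied no Month 6 data at all. The cap is 21 in Protocol 4.1 and 8.5.1, and 30 in the synopsis and SAP 5.7. Then 99 − 21 = 78 women (52 : 26) give 84% / 70%, and 99 − 30 = 69 women (46 : 23) give 79% / 65%.

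**The case against.** The other side has several fair arguments.

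- **The rules are permissive.** A site may keep such a woman, and sections 4.2.9, 8.5.3 and 4.2.8.2 lean towards doing so. This stands, and it rules out saying that 5.3 by itself ends follow-up. It still leaves retention of primary data to local choice without criteria.
- **W.3 has a purpose and should be rare.** Another product could confound the Month 6 value, and exclusion criterion E.16 bars women unwilling to stay out of other studies. A reader might infer that these withdrawals serve no purpose; the documents do not support that. Flagging the event while still measuring her keeps the information and suits an all-randomized analysis better.
- **W.2 may be refusal of the pad test itself.** Then no rewording recovers the value.

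Three stronger readings are tempting and should not be drawn.

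- **Slow recruitment as a cause of site closure.** Protocol 11.6 lists "Failure to screen subjects" among its grounds, but that section concerns stopping the study, not a rule for closing one site. A site that had reached its cap would also be an unlikely one to fail on screening.
- **The capped-site figures as the expected loss.** With up to 15 centers, the average is 99 / 15 = 6.6 women per site. Losing 6 women (62 : 31 left) gives 89.5% / 77.8%.
- **An early exit visit as the remedy.** A pad test before Month 6 is not the primary endpoint, and the SAP imputation model would not use it. Nor does the missed pelvic exam undo the safety objective: the safety endpoint is adverse event reporting, and Protocol 9.2 has sites try to follow events still present at exit.

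**Conclusion.** The point holds as an avoidable gap. After a one-time treatment, 5.3 lets women leave follow-up under W.2, W.3 or the discretionary sentence with no Month 6 measurement planned. It also conflicts with 4.2.9 on the grounds for early exit, and the discontinuation procedures mentioned in 9.3 are not defined.

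The loss of power is modest under the assumed 5 to 10% loss: about 1.4 to 3.1 points at SD 28 (91.3% to 89.8% and 88.2%) and 2.1 to 4.4 points at SD 33 (80.4% to 78.3% and 76.0%). This rests on the plan's own difference and SDs, equal loss in both arms, and imputation that recovers essentially nothing. The risk of bias is the better reason to act. It arises only if these withdrawals depend on outcome in a way that treatment, site and baseline do not explain. That is plausible, but the documents offer no figure for it.

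**What to change.** Amend Protocol 5.3 to say:

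- W.3, discretionary removal, and refusal of a procedure other than the 1-hr pad test are recorded as deviations and do not by themselves end follow-up.
- The woman is asked to attend Visit 5 and have the 1-hr pad test, unless she withdraws consent or the investigator documents a safety reason against a given procedure.
- If a single site is closed, Visit 5 is arranged where feasible for women already treated. Termination of the whole study lies outside this fix.

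Bring 4.2.9 into line with this, and either define the discontinuation procedures that 9.3 mentions or remove the reference. In SAP 5.2, state that an observed Month 6 value from such a woman enters the primary analysis in her randomized group, with the event flagged.

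The cost is a short protocol amendment and a sentence in the SAP. The visit and assessments already exist. The one drawback is that some Month 6 values will come from women who also used another product, and the flag lets these be identified.

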## **6 CONCOMITANT MEDICATIONS/THERAPIES**

Subjects will be queried regarding concomitant use of medications throughout their participation in the study until the final follow-up visit. All concomitant medication use (both prescription and over-the-counter, including herbal medications and nutritional supplements) should be reported during the study and recorded on the eCRF.

### **6.1 ALLOWED OVER-THE-COUNTER PRODUCTS AND MEDICATIONS**

The following medications will be allowed during the study:

- Vaginal moisturizers and lubricants.
- Pharmacologic agents that may impact urinary incontinence (e.g. oral estrogens, sedative-hypnotics, antidepressants, ACE inhibitors, nonsteroidal anti-inflammatory drugs and calcium channel blockers) are allowed during the study as long as the subject has been on a stable dose for  $\geq$  1 month prior to the Screening Visit and remains on a stable dose throughout study participation.
- Prescription changes for medications that do not affect urination.
- Oral or implantable birth control.
- Local vaginal hormones are allowed if the subject has been on them for  $\geq$ 6 weeks before Screening and remains on a stable dose throughout study participation.

### **6.2 PROHIBITED MEDICATIONS/THERAPIES**

Prohibited medications/treatments throughout this study include:

- Chronic use of anti-inflammatory drugs, including ibuprofen, aspirin, and steroids (excluding aspirin that is taken for cardiovascular prophylaxis).

- Taking any new medication, including herbal supplements and those taken in teas (< 1 month) that affects urination, or change in the dosage of any medication that affects urination within 1 month of Screening. Dosage should not change for the remainder of the study unless medically necessary.
- The addition of pelvic floor strengthening interventions. Subjects who have implemented pelvic floor strengthening interventions may be included if there have been no changes within the 3 months prior to screening.

## 7 LIFESTYLE GUIDELINES

### 7.1 CONTRACEPTION

Acceptable forms of birth control include: abstinence from heterosexual vaginal intercourse, hysterectomy, double tubal ligation, vasectomy, double barrier contraception, intrauterine device or hormonal contraceptive. Rhythm and withdrawal are not considered acceptable forms of contraception.

### 7.2 DIETARY RESTRICTIONS

Subjects should refrain from drinking more than 2 cups of caffeinated beverages per day on days of pad weight assessment and during the voiding diary data collection.

### 7.3 USE OF ALCOHOL, TOBACCO AND DRUGS

Subjects are required to abstain from excessive alcohol consumption the night prior to study visits and during the voiding diary collection period.

The abuse of illicit drugs or alcohol during the study is prohibited.

### 7.4 RESTRICTIONS ON PHYSICAL ACTIVITY

There are no restrictions on physical activity during the study; however, activity should be noted on the voiding diary.

## 8 INVESTIGATIONAL PRODUCT (IP) MATERIALS AND MANAGEMENT

### 8.1 TREATMENT GROUPS

There are two treatment groups in this study:

- Active Treatment Group: The active treatment group will receive a treatment dose of 90 J/cm^2.
- Sham Treatment Group: The sham treatment group will receive a sub-treatment dose of ≤1 J/cm^2.

The two tips look and behave exactly the same from the subjects and investigators (or designee) perspective. All other study procedures for the two treatment groups will remain the same.

